8.4.1 Reporting to IRB

8.4.1.1 *Unanticipated Problems*

All incidents or events that meet criteria for unanticipated problems (UAPs) as defined in Section 8.1.1 Unanticipated Problems require the creation and completion of an unanticipated problem report form (OHR-20).

UAPs that pose risk to participants or others, and that are not AEs, will be submitted to the IRB on an OHR-20 form via the eazUP system within 10 working days of the investigator becoming aware of the event.

UAPs that do not pose risk to participants or others will be submitted to the IRB at the next continuing review.

8.4.1.2 *Adverse Events*

Grade 1 AEs will be reported to the IRB at continuing review.

Grade 2 AEs will be reported to the IRB at the time of continuing review.

8.4.1.3 *Serious Adverse Events*

SAEs will be reported to the IRB on OHR-10 forms via the electronic reporting system (eSAEY) according to the required time frames described below.

Grade 3-4 AEs that are unexpected and deemed to be at least possibly related to the study will be reported to the IRB within 2 working days of knowledge of the event.

Grade 3-4 AEs that are deemed unrelated to the study will be reported to the IRB within 5 working days.

Grade 5 AEs will be reported to the IRB within one working day of knowledge of the event.

All SAEs will be submitted to the IRB at continuing review, including those that were reported previously.

8.4.2 *Reporting to SKCC DSMC*

All AEs and SAEs, safety and toxicity data, and any corrective actions will be submitted to the DSMC per the frequency described in the SKCC DSMP. The report to the SKCC DSMC will also include any unanticipated problems that in the opinion of the PI should be reported to the DSMC.

For expedited reporting requirements, see table below:

DSMC AE/SAE Reporting Requirements

	Grade 1	Grade 2		Grade 3				Grades 4 and 5
	Unexpected and Expected	Unexpected	Expected	Unexpected		Expected		Unexpected and Expected
				With Hospitalization	Without Hospitalization	With Hospitalization	Without Hospitalization	
Unrelated Unlikely	Reviewed at Quarterly DSMC Meeting and IRB Annual Review	Reviewed at Quarterly DSMC Meeting and IRB Annual Review	Reviewed at Quarterly DSMC Meeting and IRB Annual Review	5 Working Days	Reviewed at Quarterly DSMC Meeting and IRB Annual Review	5 Working Days	Reviewed at Quarterly DSMC Meeting and IRB Annual Review	Phase I - 48 Hours (Death: 24 Hours)
Possible Probably Definite	Reviewed at Quarterly DSMC Meeting and IRB Annual Review	Reviewed at Quarterly DSMC Meeting and IRB Annual Review	Reviewed at Quarterly DSMC Meeting and IRB Annual Review	48 Hours (Death: 24 Hours)	Phase I - 48 Hours	48 Hours (Death: 24 Hours)	Reviewed at Quarterly DSMC Meeting and IRB Annual Review	Phase I and Phase II - 48 Hours (Death: 24 Hours)

8.4.3 Reporting to Funding Sponsor

Once a year throughout the clinical trial, the sponsor will provide the Competent Authority with a listing of all suspected serious adverse reactions which have occurred over this period and a report of the subjects' safety. Annual reports are submitted in accordance with ICH guideline E2F - Note for guidance on development safety update reports.

8.4.4 Reporting to FDA

The PI and the SKCC regulatory team will be responsible for submitting annual reports to the FDA on the progress of the study. For event reporting, any event that is both serious and unexpected must be reported to the Food and Drug Administration (FDA) as soon as possible and no later than 7 days (for a death or life-threatening event) or 15 days (for all other SAEs) after the investigator's or institution's initial receipt of the information. Thomas Jefferson University will submit SAE reports to the FDA. The TJU Study Site Contact is responsible for submitting SAEs to the funder that occur at the affiliate site.

SAEs should be reported on MedWatch Form 3500A, which can be accessed at: <http://www.accessdata.fda.gov/scripts/medwatch/>

MedWatch SAE forms should be sent to the FDA at:

MEDWATCH
[name]
[name]
Fax: [name] ([name])
<http://www.accessdata.fda.gov/scripts/medwatch/>

- An SAE report should be completed for any event where doubt exists regarding its seriousness.
- For studies with long-term follow-up periods in which safety data are being reported, include the timing of SAE collection in the protocol.
- If the investigator believes that an SAE is not related to study drug, but is potentially related to the conditions of the study (such as withdrawal of previous therapy or a complication of a study procedure), the relationship should be specified in the narrative section of the SAE Report Form.
- If only limited information is initially available, follow-up reports are required. (Note: Follow-up SAE reports should include the same investigator term(s) initially reported.)

8.4.5 Reporting of Pregnancy

Pregnancy is an exclusion criteria and women of a child-bearing potential must use adequate protection measures. If a subject becomes pregnant during the study they will be discontinued from the study.

8.5 Halting Rules

The whole trial may be discontinued at the discretion of the PI or the sponsor in the event of any of the following:

- Occurrence of AEs unknown to date in respect of their nature, severity and duration
- Medical or ethical reasons affecting the continued performance of the trial

9 Study Oversight

In addition to the PI's responsibility for oversight, study oversight will be under the direction of the SKCC's Data and Safety Monitoring Committee (DSMC). The SKCC DSMC operates in compliance with a Data and Safety Monitoring Plan (DSMP) that is approved by the NCI.

10 Clinical Site Monitoring and Auditing

Clinical site monitoring and auditing is conducted to ensure that the rights of human participants are protected, that the study is implemented in accordance with the protocol and/or other operating procedures, and that the quality and integrity of study data and data collection methods are maintained. Monitoring and auditing for this study will be performed in accordance with the SKCC's Data and Safety Monitoring Plan (DSMP) developed by the SKCC Data and Safety Monitoring Committee (DSMC). The DSMP specifies the frequency of monitoring, monitoring procedures, the level of clinical site monitoring activities (e.g., the percentage of participant data to be reviewed), and the distribution of monitoring reports. Some monitoring activities may be performed remotely, while others will take place at the study site(s). Appropriate staff will conduct monitoring activities and provide reports of the findings and associated action items in accordance with the details described in the SKCC DSMP.

11 Statistical Considerations

11.1 Study Hypotheses

H1: Contrast reperfusion time, degree of tumor enhancement relative to the surrounding parenchyma, tumoral IFP and 3D morphological features of the vasculature quantified via CEUS before therapy correlate with SoC mRECIST reads of non-HCC tumor patients treated with TARE.

H2: mRECIST reads for non-HCC tumor patients receiving TARE combined with microbubble inertial cavitation have more complete response (CR) and partial response (PR) reads compared to the historical group treated with TARE alone.

H3: Patient's time to required next treatment and overall survival are longer for non-HCC tumor patients receiving TARE combined with microbubble inertial cavitation compared to the historical group treated with TARE alone.

H4: Observed and self-reported adverse events, and changes in liver function tests (LFTs) one month post-TARE in non-HCC tumor patients receiving TARE combined with microbubble inertial cavitation are similar compared to the historical group treated with TARE alone.

H5: Values of tumor perfusion and residual vascularity quantified by CEUS 2-4 hours, 1 week, and 2 weeks after TARE therapy are lower in CR and PR mRECIST reads of non-HCC tumor patients treated with TARE.

H6: Reductions of tumor perfusion and residual vascularity values quantified by CEUS 2-4 hours, 1 week, and 2 weeks after TARE therapy are more frequent in CR and PR mRECIST reads of non-HCC tumor patients treated with TARE.

H7: Tumoral response in mRECIST reads of MRI or CT (obtained clinically from patients treated with TARE) at 1 month post treatment will agree with response in their mRECIST reads at 3-6 months.

H8: Values of IFP quantified by SHAPE 2-4 hours, 1 week, and 2 weeks after TARE therapy are lower in CR and PR mRECIST reads of patients treated with TARE.

H9: Reductions of IFP values quantified by SHAPE 2-4 hours, 1 week, and 2 weeks after TARE therapy are more frequent in CR and PR mRECIST reads of patients treated with TARE.

11.2 Analysis Plans

In general, categorical data will be summarized as counts and percentages (or proportions) and continuous data will be summarized with descriptive statistics such as mean, standard deviation (SD), median, and range. All statistical analysis will be performed by [name] using SAS version 9.4 (Cary, NC). All statistical tests will be conducted at a nominal $\alpha=0.05$ level. For H1 (see Section 11.1 above), the respective relationships between the CEUS-derived contrast reperfusion time, degree of tumor enhancement relative to the surrounding parenchyma, tumoral IFP and 3D morphological features of the vasculature with the patients' subsequent mRECIST diagnosis (3 levels: stable disease, partial response, or complete response) will be evaluated by testing for mean difference in the CEUS measures between response levels by analysis of variance (ANOVA). Historical controls ($n=20$) will be identified from a pool of recently treated non-HCC patients at Jefferson that meet study eligibility criteria for the study and match our enrollees by propensity score based on a logistic regression model including patient age, tumor size, bilirubin and ECOG performance score and utilizing a greedy matching algorithm. Testing for the effect of radioembolization on tumor response in H2 will be conducted using non-parametric Mann-Whitney U-tests of the differences in mRECIST distributions between historical controls and enrolled patients. The difference in time-to-event endpoints (i.e., to next treatment or death, respectively) between the treated and historical control patients for H3 will be estimated and tested using Kaplan-Meier survival methods and log-rank tests. Differences in safety data will be evaluated for H4 with descriptive statistics, but not statistical hypothesis tests. A similar ANOVA approach taken for evaluating H1 will be taken for evaluating the means of CEUS measures at different times (2-4 hours, 1 week, and 2 week, respectively) of tumor perfusion and residual vascularity values between response levels to address H5 and SHAPE IFP values for addressing H8, as well as the means of changes from baseline in these measure for addressing H6 and H9. The agreement on response between mRECIST response diagnoses at 1 month and 3-6 months post-TARE will be tested using McNemar's test.

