2.1.1 Primary

To determine the ability of quantitative volumetric CEUS to predict non-HCC tumor response to TARE prior to therapy. Existing volumetric parametric imaging algorithms will also be employed to quantify vascular heterogeneity, volumetric perfusion, and area under the curve will be quantified. These variables will then be compared to modified response evaluation criteria in solid tumors (mRECIST) findings 3-6 months post treatment to identify CEUS-derived hallmarks of tumor vascularity that predict treatment response.

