2.1.2 Secondary

- To characterize the safety and preliminary efficacy of using localized UCA inertial cavitation to improve tumoral response to radioembolization.
- To determine if CEUS estimated tumor perfusion and residual vascularity 7-14 days post treatment can predict tumoral response to radioembolization.
- To evaluate tumoral response using the patient's 1 month MRI (obtained clinically) and determine the accuracy of MR or CT tumor evaluation at this earlier time point.

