2.2 Endpoints/Outcome Measures

2.2.1 Primary

Tumor complete response (CR) and partial response (PR) on mRECIST reads of contrast-enhanced CT or MRI obtained 3-6 months after treatment determined by two independent readers

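### The primary and 7-14 day objectives ask whether CEUS predicts response, but section 11.2 specifies only an ANOVA of CEUS means and no measure of discrimination

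*Combined protocol and SAP*

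**What the plan says.** - **Primary objective (section 2.1.1, and the Study Summary):** "To determine the ability of quantitative volumetric CEUS to predict non-HCC tumor response to TARE prior to therapy". The section adds that CEUS variables will be set against mRECIST to "identify CEUS-derived hallmarks of tumor vascularity that predict treatment response".
- **Secondary objective (2.1.2):** "To determine if CEUS estimated tumor perfusion and residual vascularity 7-14 days post treatment can predict tumoral response to radioembolization".
- **Primary endpoint (2.2.1):** "Tumor complete response (CR) and partial response (PR) on mRECIST reads of contrast-enhanced CT or MRI obtained 3-6 months after treatment".
- **H1 (11.1):** uses a weaker verb. The measures "quantified via CEUS before therapy correlate with SoC mRECIST reads of non-HCC tumor patients treated with TARE". H5 and H6 are framed as lower values, or more frequent reductions, in patients read as CR or PR.
- **Analysis of H1 (11.2):** "testing for mean difference in the CEUS measures between response levels by analysis of variance (ANOVA", with the outcome in "3 levels: stable disease, partial response, or complete response". A similar ANOVA serves H5 and H6. Means, SDs, medians and ranges are planned for continuous data in general.
- **Sample size (11.4):** the primary objective is sized on that ANOVA, with 20 patients split 25/50/25% and 80% power at 0.76.

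Logistic regression appears in 11.2 only for propensity matching of historical controls. Section 11.5 only refers back to the main plan.

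**The concern.** Prediction concerns how well a patient's CEUS value separates a future responder from a non-responder. An omnibus ANOVA asks whether at least one of three group means differs from the others. It takes no account of the order of the response levels. It also does not isolate CR or PR against no response, although CR and PR are the primary endpoint and H5 and H6 are worded in those terms.

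The uses foreseen in the protocol are at patient level: guiding the choice of treatment (section 1.1, Study goal) and identifying who would benefit most from TARE (1.4.2). Section 11.3.2 also wants the accuracy of the 1-month MRI or CT read so that it can be considered as an alternative to CEUS. That comparison needs an accuracy measure for CEUS, and none is planned. If an AUC is added only after the data are seen, the metric, the grouping of response levels and any cut-off would be chosen on 20 patients with several measures and visits. That invites optimistic results.

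**Working it through.** **1. The plan's own figure.** Inputs from 11.4: N = 20, groups of 5/10/5, alpha 0.05, effect 0.76. For a one-way ANOVA with 3 groups, df = (2, 17) and the noncentrality is λ = N·f². Reading 0.76 as Cohen's f gives λ = 20 × 0.76² = 11.55 and power 0.7999. The stated 80% reproduces. Four readings of 0.76 as a difference between means do not reproduce it:
- 0.76 SD between adjacent levels: 49%
- 0.76 SD from lowest to highest level: 15%
- stable disease 0.76 SD from the other two: 21%
- PR 0.76 SD from the other two: 27%

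**2. What the powered effect implies for discrimination.** Write the means in SD units, with stable disease as reference, PR higher by a and CR higher by b. λ = Σ nᵢ(μᵢ − μ̄)², held at the value that gives 80% power. For normal measures with equal SDs, the AUC for CR+PR versus stable disease is

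AUC = [10·Φ(a/√2) + 5·Φ(b/√2)] / 15.

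Worked example, linear trend (0, d, 2d): λ = 5d² + 5d² = 10d², so d = √(11.55/10) = 1.07. Then AUC = [10·Φ(0.76) + 5·Φ(1.52)]/15 = (10 × 0.776 + 5 × 0.936)/15 = 0.83.

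| Pattern of means, each with 80% ANOVA power | Separation | AUC, CR+PR v stable |
|---|---|---|
| Only stable disease differs | 1.76 SD | 0.89 |
| Linear trend | 1.07 SD per level | 0.83 |
| Only PR differs | 1.52 SD | 0.74 |
| Only CR differs | 1.76 SD | 0.63 |
| PR above and CR below stable | +0.58 and −1.28 SD | 0.50 |

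AUCs are oriented so that values above 0.5 mean separation. The last row checks as (10 × 0.659 + 5 × 0.182)/15 = 0.50.

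**3. Precision of an AUC at this sample size.** The documents give no AUC, so 0.70 to 0.90 is assumed. Hanley-McNeil, with n₁ responders and n₂ non-responders:

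SE² = [A(1−A) + (n₁−1)(Q₁−A²) + (n₂−1)(Q₂−A²)] / (n₁n₂), where Q₁ = A/(2−A) and Q₂ = 2A²/(1+A).

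At A = 0.80 with 15 v 5: Q₁ = 0.667 and Q₂ = 0.711, so SE² = (0.160 + 14 × 0.0267 + 4 × 0.0711)/75 = 0.0109 and SE = 0.104. On the logit scale, 1.386 ± 1.96 × 0.104/0.16 back-transforms to 0.53–0.93. The untransformed Wald interval is 0.60–1.00 and reaches the boundary. At 0.90 it passes it (0.76–1.04).

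| Assumed AUC | SE, 15 v 5 | Logit 95% CI, 15 v 5 | Logit 95% CI, 12 v 8 | Logit 95% CI, 10 v 10 |
|---|---|---|---|---|
| 0.70 | 0.128 | 0.41–0.89 | 0.44–0.88 | 0.43–0.88 |
| 0.80 | 0.104 | 0.53–0.93 | 0.54–0.93 | 0.53–0.93 |
| 0.90 | 0.071 | 0.66–0.98 | 0.66–0.98 | 0.64–0.98 |

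Section 1.1 cites response of 25–60% after radioembolization, which is 5 to 12 of 20 patients. The 12 v 8 column covers the upper end. At the lower end (5 v 15), the same formula at AUC 0.80 gives SE² = (0.160 + 4 × 0.0267 + 14 × 0.0711)/75 = 0.0168, SE = 0.130 and a logit interval of 0.45–0.95.

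**The case against.** The best defense is that this is a pilot whose size is set by patient availability (11.4), that 1.4.2 rules out treatment decisions based on CEUS, and that H1 and H5 are worded as correlation or difference. A comparison of means fits those hypotheses, and screening markers for association is a defensible first step. This stands as far as it goes. It makes rewording the objectives a legitimate remedy, but it does not supply a measure of prediction while the objectives keep that word.

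Three stronger readings are tempting and are not supported:

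- **The trial will yield only a p-value and nothing for planning a larger study.** Section 11.2 also plans means and SDs. It does not say that they will be given by response level, but an ANOVA report normally does so, and they would inform planning. What is missing is a stated discrimination measure with an interval. Deriving one from means and SDs needs normality and equal variances, which groups of 5 cannot check.
- **The design is powered for an AUC of about 0.70.** That figure is Φ(0.76/√2), which treats 0.76 as a difference between two groups. The 80% reproduces with 0.76 as Cohen's f, so 0.70 does not describe the powered effect. Likewise, 1.07 SD converts to 0.78 only between adjacent levels.
- **ANOVA is invalid because it groups patients by outcome, and AUC should replace it.** An AUC also compares CEUS values between outcome groups. The objection is that no discrimination statistic is named, which gives no reason to demote the powered test.

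**Conclusion.** The concern holds in this limited form. Sections 2.1.1 and 2.1.2 set prediction objectives, the only inferential analysis for H1, H5 and H6 is an ANOVA of means, and no measure of discrimination is specified. The same 80% power is compatible with AUCs from 0.50 to 0.89 in the patterns examined, so a significant F test would not by itself answer the objective. That range rests on the 5/10/5 split, normal measures with equal SDs and no progressive disease. The patterns are illustrations and do not bound what could occur. The ANOVA remains a valid test of association. The change should be made, though the trial is not unsound without it.

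**What to change.** In section 11.2, keep the ANOVA as the powered test and add:

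1. For each H1 CEUS measure, a pre-specified ROC AUC for CR+PR versus no response at 3-6 months, with a 95% CI on the logit scale or by bootstrap. An untransformed Wald interval should not be used.
2. The same for the H5 and H6 measures at each visit, labelled secondary.
3. A statement that no cut-offs will be chosen in this sample, and that no response includes any progressive disease, which the three ANOVA levels leave out.

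The alternative is to reword the primary and 7-14 day objectives as association, in 2.1 and in the Study Summary.

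The first option needs a few sentences in the plan and one further procedure on data already collected. Section 11.4 can stay sized on the ANOVA, since the AUC is an added estimate and not a new powered test. The costs are wide intervals, so the AUCs must be presented as pilot estimates only, and some loss of detail from pooling PR with CR, which the retained three-level ANOVA offsets.

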6.1 Pretreatment Period/Screening

Subjects eligible for trial enrollment will be identified by Drs. [name], [name], and [name] from their patient population (approximately 50-60 eligible patients per year recruited across 4 Jefferson Health campuses and treated in our main Center City Hospital in Philadelphia). Patients will be accrued from the Hepatology department, Interventional Radiology, and the

Multidisciplinary Liver Tumor Board of the Sidney Kimmel Cancer Center at Thomas Jefferson University.

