11.4 Sample Size Considerations

Sample size for this pilot study is primarily driven by patient availability and larger, multi-center randomized trials will likely be needed to fully demonstrate efficacy. However, for the primary objective, a sample size of 20 patients (of which we expect 25% having stable disease, 50% partial responders, and 25% complete responders) will provide 80% power to detect a 0.76 standard deviation difference in CEUS measurement means (e.g., mean contrast perfusion time) between mRECIST response levels, by analysis of variance (ANOVA) with a nominal 5% type I error rate. Similarly, in analyses comparing the prospective treated patients to matched historical control patients, 20 patients per arm will provide 80% power to detect a relative effect size of 0.66 standard deviations by t-test with a nominal 5% type I error rate (i.e., a moderately large, but reasonable effect given our current data in HCC patients).

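### The 80% power stated for the historical-control comparison holds only for a paired t-test, while the planned tests are unpaired (about 53% for 20 v 20), and the cap of 20 controls is unexplained

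*Combined protocol and SAP*

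**What the plan says.** Section 11.2 sets the size and source of the control group: "Historical controls ($n=20$) will be identified from a pool of recently treated non-HCC patients at Jefferson". Controls must meet the study's eligibility criteria. They are matched to enrollees by a greedy algorithm on a propensity score built from age, tumor size, bilirubin and ECOG score. With 20 enrollees this is one control each, although the ratio is not written out.

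The tests in section 11.2 are for independent groups. For H2: "Testing for the effect of radioembolization on tumor response in H2 will be conducted using non-parametric Mann-Whitney U-tests". For H3 the time-to-event differences "will be estimated and tested using Kaplan-Meier survival methods and log-rank tests". H4 is descriptive, with no hypothesis tests.

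Section 11.4 gives the power for the comparison of enrollees with their matched controls: "20 patients per arm will provide 80% power to detect a relative effect size of 0.66 standard deviations by t-test". It does not say whether the t-test is paired, or one- or two-sided. It attributes the sample size mainly to patient availability.

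On supply, section 6.1 mentions "approximately 50-60 eligible patients per year recruited across 4 Jefferson Health campuses", as a source for prospective enrolment. No section gives the size or calendar window of the historical pool.

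**The concern.** There are two linked problems.

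- **Power basis.** The effect size and power in section 11.4 fit a paired analysis, but the analyses in section 11.2 discard the pairing. A reader of 11.4 would think the secondary efficacy comparison far better powered than it is, and could read a null H2 result as stronger evidence against an effect than it would be.
- **Control number.** Patient availability explains 20 enrollees. It does not by itself explain 20 controls, who have already been treated and need no consent visit, contrast infusion or ultrasound session. With equal groups, half the sampling variance of a mean difference comes from the controls. That half can be reduced without exposing anyone to the intervention.

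**Working it through.** **Inputs.** From section 11.4: 20 per arm, 0.66 SD, 5% type I error, 80% power. From section 11.2: 20 controls and unpaired tests. Two-sided testing is my assumption.

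**Step 1: reproduce the stated 80%.** Power comes from the noncentral t distribution.

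- Paired, 20 pairs: noncentrality = 0.66 × √20 = 2.952; 19 df; critical value 2.093. Power = **79.9%**, which matches. Here 0.66 is in SDs of the within-pair difference. That equals 0.66 outcome SDs only if the within-pair correlation is 0.5, because SD of difference = SD × √(2(1 − ρ)).
- Unpaired, 20 v 20: noncentrality = 0.66 / √(1/20 + 1/20) = 2.087; 38 df; critical value 2.024. Power = **53.0%**. One-sided it is 65.7%, which does not match either.
- Paired test with lower correlation, 0.66 outcome SDs: 60.0% at ρ = 0.2 and 50.9% at ρ = 0.

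Unpaired, 80% power needs 0.91 SD at 20 v 20, or 38 per arm at 0.66 SD.

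**Step 2: more controls, fixed ratio, independent groups, 20 enrollees.** Noncentrality = 0.66 / √(1/20 + 1/n₂).

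| Controls | 1/20 + 1/n₂ | Noncentrality | Power at 0.66 SD | Effect for 80% power |
|---|---|---|---|---|
| 20 | 0.100 | 2.087 | 53.0% | 0.91 SD |
| 40 | 0.075 | 2.410 | 65.9% | 0.78 SD |
| 60 | 0.0667 | 2.556 | 71.4% | 0.73 SD |

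The variance of a mean difference falls by 25% (1:2) or 33% (1:3). Even 1,000 controls give only 83.1%.

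On the paired basis with ρ = 0.5, the variance factor 1 + (1 + (m − 1)ρ)/m − 2ρ is 1, 0.75 and 0.667 for m = 1, 2 and 3 controls. Power is 79.9%, 89.8% and 92.9%, a gain of 10 to 13 points.

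**Step 3: H2 by Mann-Whitney on three response levels.** Enrollees follow the 25/50/25 split of stable, partial and complete response in section 11.4. The control CR+PR rate ranges over the 25-60% by mRECIST quoted in section 1.1; its 2:1 split between PR and CR is my assumption. Simulated power:

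| Control CR+PR | 20 controls | 40 | 60 | Gain (points) |
|---|---|---|---|---|
| 25% | 88% | 96% | 98% | 8-10 |
| 40% | 55% | 69% | 75% | 14-20 |
| 50% | 31% | 39% | 44% | 8-13 |
| 60% | 14% | 17% | 18% | 3-4 |

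Simulation error and the choice of tie or continuity correction move these by about a point.

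If instead the controls are shifted by 0.66 SD on a latent scale, power is 43%, 57% and 61%.

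**Step 4: H3 by log-rank.** No hazard ratio or event count is given. Assuming a hazard ratio of 0.5-0.6 and events in 50-90% of patients, power at 1:1 is 21-55%. Two to three controls per enrollee add about 5 to 17 points.

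**Step 5: why a variable ratio gives less.** With matched-set weights, the control mean has variance proportional to (1/20²) × Σ(1/mᵢ). Suppose 10 enrollees have one control and 10 have three, so 40 controls in all. The sum is 10 + 3.33 = 13.33, and 13.33/400 = 0.0333 = 1/30. Those 40 controls count as 30, and power at 0.66 SD is 61%, not 66%.

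**The case against.** The case for leaving the plan alone has several parts.

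- **The comparison is described as matched, and the paired calculation is exact.** This stands in part: the figure is not a slip of arithmetic. But section 11.2 names unpaired tests, and no within-pair correlation is given or justified. The two sections describe different analyses.
- **The supply of controls is inferred.** This stands. A reader might multiply the 50-60 patients a year in section 6.1 by two years and conclude that 80-100 usable candidates are being discarded. The documents do not support that. The figure is a prospective estimate. Controls must be recently treated, must have had a previously untreated tumor that fits the ultrasound 3D volume (a scan that patients given TARE alone may not have), must match on the score and must have 3-6 month imaging.
- **One headline gain misleads.** This stands. A reader might infer that the design gives up 13 to 18 points of power throughout. That range applies only to an unpaired t-test at 0.66 SD, from a base of 53%. It is 10 to 13 points on the paired basis and varies widely for H2 and H3.
- **More controls do not repair the comparison.** This stands. At 0.66 SD even 1:3 falls short of 80%. Bias from using historical controls remains, and a longer window weakens recency.
- **This is a pilot with a secondary aim of preliminary efficacy, and 1:1 matching is a legitimate choice.** Fair, and it limits the weight of the point. But the plan tests H2 and H3 at the 5% level and quotes power for this comparison, so the quoted power should fit the tests.

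**Conclusion.** The power statement in section 11.4 does not describe the analyses in section 11.2. For an unpaired two-sided t-test on 20 v 20, power at 0.66 SD is about 53%, and the effect detectable with 80% power is 0.91 SD. This needs no assumption beyond two-sided testing, and one-sided testing does not rescue the stated figure.

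The cap of 20 controls is an unexplained choice that could be improved, not an error. At 0.66 SD, two or three controls per enrollee would bring power to at most about 66% or 71%. This assumes that enough close matches exist, and a weighted variable-ratio match would give somewhat less. The gap would be only partly closed. The benefit for H2 is smallest where control response is high and power is already poor. H4 gains precision but no test power. H3 is expected by section 11.3.2 to outlast the study's timeline. H1, analysed within the 20 enrollees, is untouched. The point should be addressed but does not threaten the primary objective.

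**What to change.** 1. **Section 11.4.** Replace the 80% at 0.66 SD with figures for an unpaired comparison: with 20 per group, a two-sided 5% t-test has about 53% power at 0.66 SD and 80% power at 0.91 SD. If another ratio is adopted, give its detectable effect (at best 0.78 SD at 1:2 or 0.73 SD at 1:3) and label it as an upper limit on performance.
2. **Section 11.2, control group.** Replace the fixed 20 with up to two or three controls per enrollee. Draw them from all consecutive eligible past patients in a stated recent window, and report the pool size. Take a second or third control only if it lies within a pre-set propensity caliper. If close matches run out, the ratio falls back towards 1:1. If 1:1 is kept, state why.
3. **Section 11.2, analyses.** For H2 and H3, name methods that allow for the variable ratio, such as matched-set weights with robust standard errors in an ordinal response model and a Cox model. Plain Mann-Whitney and log-rank tests do not carry such weights. Use the same weighting in the H4 summaries.

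**Cost.** Plan wording, chart abstraction for up to 20-40 more past patients, and the same number of existing scan sets read by the same two readers. Second and third matches will be somewhat less close, which the caliper limits. No one further is enrolled or treated.
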